To guide the choice of surgical technique outcomes of mortality, adverse events and self-reported quality of life are important to report. As before mentioned LARS has significant impact on quality of life and is thus important to study. In order to evaluate the underlying mechanisms of LARS, and in the future provide effective treatments, it is central to evaluate the anorectal muscle function. Anorectal muscle function has been evaluated with anorectal manometry in patients who have been treated with low anterior resection at a median of 6 weeks (range 4-40 weeks) [12] and at a mean of 23 months (range 6-106 months) [13, 14] after surgery

Sexual dysfunction, urinary incontinence and fecal incontinence are present in patients with rectal cancer as long after surgery as 4 years, therefore it is important to determine if when these symptoms develop and how they are related to each other in patients treated for rectal cancer. [18] To our knowledge, no records exist on these relationships from prior to surgery to 2 years after low anterior resection. This type of information is central to the future design and conduct of expensive randomized trials.

Purpose

The primary purpose of the EDFI-Cohort study is to determine how several baseline variables (surgical technique, anorectal muscle function, faecal incontinence, urinary incontinence, sexual dysfunction, fatigue, physical activity, meaning in life and physical functioning) develop over time and predicts quality of life, and secondary how it predicts LARS-score in patients with rectal cancer from prior to surgery to 2 years after primary treatment.

Hypothesis

A priori, we determined the following major hypotheses for this study to be (with corresponding null hypotheses):

1. We expect to see poorer quality of life in patients with a higher LARS-score
2. Overall we expect to see poorer quality of life in patients with poor anorectal muscle function, faecal incontinence, urinary incontinence, sexual dysfunction, fatigue, low physical activity, low meaning in life and physical functioning.
3. We expect to a difference in quality of life and LARS-scores between surgical technique. We expect that PME will lead to fewer symptoms and TA-TME to worse symptoms compared with other techniques.
4. We expect to see no differences in mortality rate and adverse events between the different baseline variables.

Method

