Subjects for the EDFI-Cohort study will be recruited during 2019 and 2020 from Department of Surgery, Slagelse, and Zealand University Hospital, Køge. Subjects need to be diagnosed with rectal cancer and have received curative surgery (low anterior resection) with/without adjuvant (radiation/chemo) therapy. Subjects for this study are to meet the following inclusion criteria: Low anterior resection (e.g. not limited to total mesorectal excision (TME) or partial mesorectal excision (PME)), ability to communicate in Danish, adults (> 18 years of age), and American Society of Anaesthesiologists (ASA) score: I-IV. Exclusion criteria are: ASA score of: V-VI.

Prior to inclusion, subjects must provide written informed consent to participate in this study.

Subjects for the EDFI-Cohort study will be identified through surgical codes at Slagelse Hospital and Zealand University Hospital, Køge, Denmark. Eligible subjects will primarily be invited to participate in this study prior to discharge with oral and written information, provided in person by a health professional from the research group. Alternatively eligible subjects will be sent a letter after discharge. The letter and written information contain information on the study, the right to say no to the study, the right to 24 hours reflection time and the right to bring next of kin or another person of the subject's choice with him/her to the inclusion meeting. Potential subjects that are only invited by letter are asked to contact the research group for further information. A second letter will be sent to potential subjects whom have not contacted the research group within two weeks, and 2-3 weeks after the second letter has been sent, subjects will be contacted once by phone. Verbal and written information will be provided by a health professional from the research group at a meeting in an undisturbed examination room at Slagelse Hospital or Zealand University Hospital, Køge, Denmark.

Sample size:

The cohort will recruit all eligible patients from summer 2019 to April 2020. In this time period we estimate to recruit 70 patients to the EDFI cohort. A total of 86 patients were surgically treated for rectum cancer in 2017 at Slagelse Hospital and Zealand University Hospital, Køge.

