The minimal clinically important difference on the EORTC QLQ-C30 subscale Global Health Status is considered to be 7-12 points for a variety of cancer types (rectal cancer not studied). [19-22] Thus, with the estimated recruitment flow; we will have a power of 0.98 for a two-sample pooled t-test of a normal mean difference with two-sided significance level of 0.05 ($p \leq 0.05$), assuming a common SD of 22 EORTS QLQ-C30 points to detect a mean difference of 10 points between groups with different surgical techniques or with high or low anorectal muscle function (primary study purpose 1).

Additionally, we will have a power of 0.99 for a two-sample pooled t-test of a normal mean difference with two-sided significance level of 0.05 ($p \leq 0.05$), assuming a common SD of 12 LARS points [3] to detect a mean difference of 6 LARS points between groups with different surgical techniques or with high or low anorectal muscle function (study purpose 2).

Whether or not we are able to reach sufficient numbers within the 1 year timeframe, recruitment will end in April 2020.

Outcomes:

Outcomes is to be obtained from patient records, self-reported questionnaires and objective measures. For full list of outcomes to be collected and time points, see table 1.

Patient records:

In order to identify and invite eligible subjects, information on diagnosis, type of surgery, admission and contact information will be collected from patient records and given to the research group, prior to acceptance to participate in the study. After acceptance to participate in this study the following descriptive information will be collected from patient records (including electronic patient journals): Age at surgery (years), time of surgery (weeks), type of surgery, surgical complications, gender (male/female), tumor height (cm from anal verge), tumor stage (UICC), involvement of lymph nodes (N stage), additional radiotherapy/chemotherapy, surgical technique, anastomosis, ASA grade (I-IV), time with temporary stoma, and if available data from pre-surgery manometric examination, digital examination, Six-Minute Walk test (6MWT) and mortality status. This information will be used to adequately describe patient characteristics, cancer treatment, surgical outcome and mortality status. Additionally the acceptance to participate in this study allows the research group and relevant control agency direct access to collect information on health status in relation to quality control.

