This study is partially funded. Funding has so far come from the local research fund of NSR hospitals (DKK 968,000) and The Association of Danish Physiotherapists (DKK 82,000). The Department of Physiotherapy and Occupational Therapy at Slagelse Hospital provides access to facilities and offices. None of the funding agencies have any influence on study design or reporting of data. Further funding will be applied for from public and private foundations.

To reduce unnecessary inconvenience for subjects, we have planned the study test sessions on same days as subjects are to meet in the LARS outpatient clinics.

Dissemination of study results:

The EDFI-Cohort study is expected to be presented at several conferences for health professionals and the public and to provide 4 international peer-reviewed scientific papers on the findings whether they are positive, negative or inconclusive. All reporting of the EDFI-Cohort study will comply with the STROBE-guidelines [40, 41].

The first publication (paper 1) will report on associations between quality of life and LARS-score, adjusted for baseline variables (surgical technique, anorectal muscle function, faecal incontinence, urinary incontinence, sexual dysfunction, fatigue, physical activity, meaning in life and physical functioning) from prior to curative surgery until 12 weeks after surgery.

The second publication (paper 2) will report on the development of quality of life and LARS-score, stratified based on choice of surgical technique prior to curative surgery until 6 months after surgery.

The third publication (paper 3) will report on associations between quality of life and LARS-score, adjusted for baseline variables (surgical technique, anorectal muscle function, faecal incontinence, urinary incontinence, sexual dysfunction, fatigue, physical activity, meaning in life and physical functioning) from prior to curative surgery until 2 years after surgery.

The fourth publication (paper 4) will report on mortality rate and adverse events adjusted for baseline variables (surgical technique, anorectal muscle function, faecal incontinence, urinary incontinence, sexual dysfunction, fatigue, physical activity, meaning in life and physical functioning) from prior to curative surgery until 2 years after surgery.

References

1. Annual report 2017, in *Danish Colorectal Cancer Group*, D.C.C. Group, Editor. 2017, The Danish Clinical Registries and Danish Multidisciplinary Cancer Groups.

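### Paper 4 reports mortality from before surgery onwards, but deaths between surgery and consent cannot enter the cohort, so mortality dated from surgery is biased low

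*Protocol*

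**What the plan says.** **Reporting window.** Under Dissemination of study results: "The fourth publication (paper 4) will report on mortality rate and adverse events adjusted for baseline variables". The list of those variables ends with "meaning in life and physical functioning) from prior to curative surgery until 2 years after surgery".

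**Hypothesis 4.** "We expect to see no differences in mortality rate and adverse events between the different baseline variables".

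**Entry (Method).** "Subjects need to be diagnosed with rectal cancer and have received curative surgery (low anterior resection"), and "Subjects for the EDFI-Cohort study will be identified through surgical codes". Written consent precedes inclusion. On timing, "Eligible subjects will primarily be invited to participate in this study prior to discharge with oral and written information"; otherwise a letter goes out after discharge, a second letter follows after two weeks without contact, and "2-3 weeks after the second letter has been sent, subjects will be contacted once by phone". The only exclusion is ASA V-VI.

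**Data collection (Outcomes, Patient records, and Table 1).** Before acceptance, "information on diagnosis, type of surgery, admission and contact information will be collected from patient records and given to the research group". Surgical complications, surgical technique and mortality status are taken from records only after acceptance. Table 1 takes hospitalisation and surgical complications at 30 days after surgery. It has mortality checked when a questionnaire goes unanswered or a visit is missed.

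**The concern.** The stated window opens before surgery, but membership of the cohort depends on being alive and consenting some time after it. For mortality, the interval from surgery to consent is immortal time: every enrolled patient has survived it by definition. Perioperative deaths fall in that interval, and the design has no route by which to see them.

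The Background calls mortality and adverse events important to report when choosing a surgical technique, and hypothesis 4 expects no differences in them. A result of no difference from this cohort says nothing about deaths before consent. A two-year mortality figure labelled as running from surgery would be too low for the population a reader would take it to describe.

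**Working it through.** The protocol gives no mortality rate, complication rate or power for paper 4, so there is no figure to reproduce. The timing comes from the protocol. Every rate below is an assumption.

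**1. Timing on the letter route.** Two weeks to the second letter plus 2-3 weeks to the phone call: 14 + 14 = 28 to 14 + 21 = 35 days after the first letter. If that letter goes out on the day of discharge, and discharge is on day 5-14 (assumed), the call falls on day 5 + 28 = 33 to day 14 + 35 = 49 after surgery. Those patients have outlived the whole 30-day window before entry. Patients recruited before discharge have a shorter interval, but it is never zero.

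**2. Mortality level.** Let e be the risk of death before consent and l the risk from then to two years among those alive at consent. Assume enrolment is otherwise unrelated to later death.

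- True risk from surgery = e + (1 - e) × l. Observed risk = l. Relative shortfall = 1 - l / true.
- e = 1%, l = 15%: true = 0.01 + 0.99 × 0.15 = 0.1585; shortfall 5.4%.
- e = 2%, l = 10%: true = 0.02 + 0.98 × 0.10 = 0.118; shortfall 15.3%.
- e = 5%, l = 5%: true = 0.05 + 0.95 × 0.05 = 0.0975; shortfall 48.7%.

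In deaths, 86 × 0.01 = 0.86 to 86 × 0.05 = 4.3 would go unseen per 86 operated patients. The 86 is the protocol's 2017 count of all rectal cancer operations at the two hospitals, so it is only a rough denominator.

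**3. Mortality comparisons, group A versus group B.**

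| e (A, B) | l (A, B) | True risk (A, B) | True RR (B/A) | Observed RR |
|---|---|---|---|---|
| 1%, 5% | 10%, 10% | 10.9%, 14.5% | 1.33 | 1.00 |
| 2%, 2% | 8%, 16% | 9.84%, 17.68% | 1.80 | 2.00 |
| 5%, 1% | 8%, 12% | 12.6%, 12.88% | 1.02 | 1.50 |

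The first row moves to the null, the second away from it, and the third shows a difference where there is almost none.

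**4. Complications.** Let p be the true 30-day proportion and r the chance that a patient with a complication enrols, relative to one without. Observed proportion = p × r / (p × r + 1 - p). Take true proportions of 20% and 35% (difference 15 points, RR 1.75, OR 2.15).

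- r = 0.5 in both groups: 11.1% and 21.2%; difference 10.1 points, RR 1.91, OR 2.15.
- r = 0.7 in both groups: 14.9% and 27.4%; difference 12.5 points, RR 1.84, OR 2.15.
- True 15% in both groups, r = 0.5 and 0.9: 8.1% and 13.7%, a spurious difference.

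Equal under-enrolment shrinks the risk difference, raises the risk ratio and leaves the odds ratio alone. Unequal under-enrolment can create a difference.

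**The case against.** **The window may describe a reporting period, not a time origin.** Papers 1 and 3 use the same phrase, the statistical section names only linear models for continuous data, and the choice of origin could sit in a statistical analysis plan that is not shown. It is fair that no survival model is specified. But the entry route, the trigger for looking up deaths and the reporting period are all fixed in the protocol, and no later analysis plan can recover deaths that were never collected.

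**A reader might infer that severe complications are excluded by design too.** The documents do not support that. Such patients meet the criteria, and the main route recruits during the admission, where a patient kept in by a complication remains reachable. Complications before consent are retrieved from records once the patient accepts. They are lost only if the patient dies first, cannot consent or declines. Immortal time is therefore a problem for death, not for complications.

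**A reader might also infer that the bias favours hypothesis 4.** That does not follow: the illustrations above go both ways, and even equal under-enrolment moves the risk ratio away from the null.

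**Scale.** The 28-35 days apply only to letter-route patients who have to be phoned, and their share is not stated. With 70 patients split 35/35 (assumed), the 95% half-width for 35% versus 20% is 1.96 × √(0.35 × 0.65/35 + 0.20 × 0.80/35) ≈ 21 points, well above the 2.5-5 point shrinkage shown. This stands for the complication comparison. It does not excuse a mortality figure whose bias has a known direction.

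**Place in the study.** The stated Purpose concerns quality of life and then the LARS score; paper 4 is secondary. That limits the weight of the point.

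**Conclusion.** The point holds for mortality. Deaths between surgery and consent are excluded by design, so mortality dated from surgery is biased low. The direction follows from the protocol alone. The size does not: a relative shortfall of about 5% to 49% rests on assumed pre-consent mortality of 1-5% and later mortality of 5-15%.

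For 30-day events, under-representation of severely ill patients is plausible but unquantified. For comparisons between groups, the direction of bias is unknown. Hypothesis 4 therefore cannot be read from this cohort as covering perioperative deaths, whichever way the result falls.

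**What to change.** In the description of paper 4:

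- Count mortality time at risk from consent, with delayed entry on the time-since-surgery scale, or from a fixed landmark. A landmark must not precede consent; anyone who consents after it still needs delayed entry.
- Restate the window and the estimate as conditional on survival to enrolment.
- Present 30-day hospitalisation and complications as descriptive among enrolled patients, and state that a finding of no difference does not cover perioperative deaths.
- Report numbers operated, invited and enrolled by type of surgery, from the identification list. Add deaths before invitation only if approvals allow. The protocol does not show that these are on the list: mortality status, complications and surgical technique (listed separately from type of surgery) are collected only after acceptance.

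The cost is protocol wording, a consent date in the data set, one analysis setting and a few aggregate counts. Any count of deaths among patients not enrolled may need further approval; the protocol says this version has to go back to the ethics committee and the data protection agency in any case. The downside is that the reported mortality applies only to patients who survived to enrolment. Delayed entry removes the immortal time but not any selection by illness among those who survive.

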Self-reported outcomes:

Information on education level, work status and civil status will be obtained through self-reported questionnaires at 3 weeks. The remaining self-reported outcomes is collected with a series of validated questionnaires that subjects will be asked to complete 6 times during the two year study, see table 1.

Quality of life of cancer patients (primary outcome) is assessed with questionnaires developed by the European Organisation for Research and Treatment of Cancer (EORTC). EORTC has developed and validated a generic core set (EORTC QLQ-C30) for assessing quality of life. [23] [24] As recommended by the EORTC, have added symptom specific module (EORTC QLQ-CR29) [23] and fatigue module (EORTC QLQ-FA12). [25] [26]

Bowel related quality of life (secondary outcome) is quantified with the Low Anterior Resection Symptom score (LARS-score), which is a validated score to group subjects into either no/low LARS or major LARS. [9] The items included in the LARS-score have been selected and weighted to reflect bowel related quality of life. [9] [27]

Faecal incontinence is also quantified with the St. Marks Incontinence score (also known as the Vaizey score), which is a validated instrument for assessing severity of faecal incontinence. [28]

Urinary incontinence is assessed with questionnaires developed by the workgroup International Consultation on Incontinence Modular Questionnaire (ICIQ). ICIQ has developed and validated a generic core set (ICIQ-UI) for assessing urinary incontinence. [29] Additionally, we use symptom specific modules also developed and validated by ICIQ. The modules assess urinary symptoms in males and females and sexual matters in males and females.

Physical activity level is quantified as done in the Danish National Health Profile – Health of the Danish People, which is a nationwide questionnaire answered by more than 180.000 Danish people in 2017. [30, 31]

Sources of meaning and meaningfulness is assessed with Sources of Meaning and Meaning in Life Questionnaire (SoMe), which is a self-reported measure of meaningfulness and crisis of meaning reported on two separate scales, enabling further analysis and comparisons of positive and negative aspects of meaning in life. The questionnaire has been validated in a Danish population. [32] [33]

Objective measures

All objective measures are to be collected at Slagelse Hospital and Zealand University Hospital, Køge, at 6 weeks, 6 months, 12 months and 24 months.

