Digital examination of anorectal muscle function is an easy-to-use and cheap assessment tool readily available in a clinical setting. When using the Digital Rectal Examination Scoring System (DRESS) that ranges 0-5 (lowest to highest), the digital examination showed very high agreement with manometry pressures (Spearman rank correlation coefficients 0.81-0.82). [34] Digital examination involves inserting a finger in the anal canal.

High-Resolution AnoRectal Manometry (HR-ARM) is considered state of art in measuring anorectal muscle function and has shown to have moderate to high reliability in adults with or without faecal incontinence, with intra-individual correlations (ICC) for resting pressure (ICC 0.60-0.91) [35] [36] [16], squeezing pressure (ICC 0.49-0.95) [35] [36] [16] and rectal perception (ICC 0.75-0.92) [36] [16]. HR-ARM involves a narrow catheter being inserted in the anal canal that measures pressure with strain gauges several times throughout the anal canal. Rectal perception is measured by inflating a balloon in the rectal canal.

The Six-Minute Walk test (6MWT) is a widely used measure of submaximal exercise capacity in populations with and without pathology. [37] The 6MWT has shown to be correlated to maximum exercise capacity ($r=0.67$) and to perceived physical function (EORTC QLQ-C30 physical function subscale) ($r=0.55$) in cancer patients. [38] A systematic review has recommended that a minimal clinically important difference of ≥ 30.5 m for the 6MWT can be considered clinically meaningful for patients with a variety of pathology. [39] 6MWT involves the patient walking as far as possible in 6 minutes indoor.

Table 1: Full list of outcomes.

Patient records at hospital	Items that is obtained	Time point
Descriptive information:	Age at surgery (years) Time of surgery (weeks) Gender (male/female) Tumor height (cm from anal verge) Tumor stage (UICC) Involvement of lymph nodes (N stage) Additional radiotherapy/chemotherapy Surgical technique Anastomosis ASA grade (I-IV) Time with temporary stoma Manometric examination (if available) Digital examination (if available) Six-Minute Walk test (if available)	At identification of relevant patients
Adverse events from surgery	Hospitalisation 30 days after surgery Surgical complications	30 days after surgery
Mortality (and at the National Patient Registry)	Is the subject deceased?	If no answer is obtained through questionnaires or no show at clinical examination.

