Self-reported outcomes:	Questionnaire	Time point
Education level, work status and civil status	Non standardized questionnaire	3 weeks
Bowel related quality of life	Low anterior resection symptom – score (LARS-score)	3, 6, 12, 26, 52 and 104 weeks
Faecal incontinence	St. Marks Incontinence score (Vaizey-score)	3, 6, 12, 26, 52 and 104 weeks
Quality of life of cancer patients:	EORTC QLC-C30	3, 6, 12, 26, 52 and 104 weeks
Colorectal	EORTC QLQ-CR29	3, 6, 12, 26, 52 and 104 weeks
Fatigue	EORTC QLQ-FA12	3, 6, 12, 26, 52 and 104 weeks
Information about disease and treatment	EORTC QLQ-INFO25	3, 6, 12, 26, 52 and 104 weeks
Urinary Incontinence	International Consultation on Incontinence Modular Questionnaire (ICIQ) - Urinary Incontinence Short Form (ICIQ-UI SF)	3, 6, 12, 26, 52 and 104 weeks
Urinary symptoms, males	ICIQ-Male Lower Urinary Tract Symptoms (ICIQ-UI MLUTS)	3, 6, 12, 26, 52 and 104 weeks
Urinary symptoms, females	ICIQ-Female Lower Urinary Tract Symptoms (ICIQ-UI FLUTS)	3, 6, 12, 26, 52 and 104 weeks
Sexual dysfunction		

	Sexual dysfunction, males	ICIQ-Male Sexual Matters associated with Lower Urinary Tract Symptoms (ICIQ-UI MLUTSsex)	3, 6, 12, 26, 52 and 104 weeks
	Sexual dysfunction, females	ICIQ-Female Sexual Matters associated with Lower Urinary Tract Symptoms (ICIQ-UI FLUTSsex)	3, 6, 12, 26, 52 and 104 weeks
	Physical activity level	physical activity section of the Danish National Health Profile	3, 6, 12, 26, 52 and 104 weeks
	Sources of meaning and meaningfulness	Sources of Meaning and Meaning in Life Questionnaire (SoMe)	3, 6, 12, 26, 52 and 104 weeks

Objective measure:	Units:	Time point
Anorectal muscle function (digital examination)		
Maximal resting pressure Maximal squeeze pressure Endurance squeeze - max squeeze pressure or longest time Latency (rate of force development), number of rectal muscle contractions/squeezes in 15 sec test.	0-5 (DRESS) (lowest to highest) 0-5 (DRESS) (lowest to highest) 0-5 (DRESS) and s, maximum of 60 s. n	6, 26, 52 and 104 weeks
Anorectal muscle function (High-Resolution AnoRectal Manometry)		
Pressure measurements: Maximal resting pressure Maximal squeeze pressure Maximal squeeze pressure duration	mmHg mmHg s	6, 26, 52 and 104 weeks
Volume capacity measurements: Maximal tolerated volume Conscious rectal sensitivity threshold Conscious rectal sensitivity Constant sensation	mL mL % of maximal volume mL	6, 26, 52 and 104 weeks
Physical Performance		
6-Minute Walk test	M	6, 26, 52 and 104 weeks

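### Paper 4 adjusts adverse events for nine baseline variables, but eight of the nine are first scheduled three or six weeks after surgery

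*Protocol*

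**What the plan says.** Under Dissemination of study results, paper 4 "will report on mortality rate and adverse events adjusted for baseline variables (surgical technique, anorectal muscle function" and seven further items: faecal incontinence, urinary incontinence, sexual dysfunction, fatigue, physical activity, meaning in life and physical functioning. The period given runs from before surgery to two years after it. Hypothesis 4 uses the same label and expects no differences in mortality or adverse events across these variables.

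Table 1 has one entry for adverse events, "Hospitalisation 30 days after surgery Surgical complications", with its time point at 30 days after surgery. The questionnaires are scheduled at "3, 6, 12, 26, 52 and 104 weeks", and the Self-reported outcomes section says that "subjects will be asked to complete 6 times during the two year study". The Objective measures section places anorectal examination and the walk test "at 6 weeks, 6 months, 12 months and 24 months".

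On entry, the Method section states: "Subjects need to be diagnosed with rectal cancer and have received curative surgery". The only pre-operative measurements mentioned come from patient records: "if available data from pre-surgery manometric examination, digital examination, Six-Minute Walk test (6MWT").

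**The concern.** A baseline variable should describe the patient before the outcome can occur and before the exposure can act. Here the outcome window opens at surgery, while eight of the nine variables are first measured after it. Two problems follow.

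- **Reverse causation.** A complication in the first weeks can worsen continence, fatigue, activity or sphincter function at week 3 or week 6. An association would then be reported as poor baseline function predicting the complication. The protocol itself points to this causal direction: its Statistical analysis section lists surgical complications, with nerve damage and sphincter rupture as examples, among the confounders to adjust for when function and quality of life are studied.
- **Adjustment for consequences of technique.** Hypothesis 3 expects PME to give fewer symptoms and TA-TME more. Adjusting a technique comparison for early post-operative symptoms conditions on something that technique is expected to change.

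At stake are the adverse-event half of paper 4 and the matching half of hypothesis 4. Mortality has a related difficulty: a patient who dies before week 3 or week 6 never has the covariate value.

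**Working it through.** The protocol gives no figure to reproduce. The check sets each of the nine variables against its first scheduled time and compares that with the 30-day window.

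**Time origin.** Table 1 does not say what its weeks are counted from. The description of paper 1 counts 12 weeks from surgery, so surgery is the natural origin. A later origin, such as discharge or inclusion, would move every measure later and make the problem worse.

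**Which adverse events.** Paper 4 does not define them. Table 1 lists only the 30-day item, so that item is used here.

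**Conversion.** Week 3 is 3 × 7 = day 21, which is before day 30. Week 6 is 6 × 7 = day 42, which is 42 − 30 = 12 days after the window closes.

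| Variable | First scheduled | Day | Relative to the 30-day window |
|---|---|---|---|
| Surgical technique | surgery (records) | 0 | fixed at the start |
| Faecal incontinence | week 3 | 21 | inside |
| Urinary incontinence | week 3 | 21 | inside |
| Sexual dysfunction | week 3 | 21 | inside |
| Fatigue | week 3 | 21 | inside |
| Physical activity | week 3 | 21 | inside |
| Meaning in life | week 3 | 21 | inside |
| Anorectal muscle function | week 6 | 42 | 12 days after |
| Physical functioning | week 3 or week 6 | 21 or 42 | inside or 12 days after |

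The last row has two readings. Table 1 lists the six-minute walk test under physical performance (week 6), while the text also refers to "perceived physical function (EORTC QLQ-C30 physical function subscale"), which belongs to a week-3 questionnaire. The split is 6 variables at week 3 and 2 at week 6, or 7 and 1. Either way, 8 of 9 are first scheduled after surgery.

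**Could there be an unlisted pre-operative questionnaire?** Six completions are planned and six time points are listed, all from week 3 onward: 6 − 6 = 0 left for before surgery. Entry after surgery is consistent with that.

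**Could the records fill the gap?** Pre-surgery manometry, digital examination and walk test bear on at most two of the eight variables, and only where they happen to exist.

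**The case against.** The strongest reply is that paper 4 never mentions 30 days. Its stated period runs to two years, so the 30-day window is borrowed from Table 1. That is correct, and the reading is an inference. It stands as the likely one because no later collection of adverse events is scheduled.

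A second reply is that one sentence in a publication plan is not a model, and that the details may sit in an SAP. The Statistical analysis section allows both simple and multiple regression, and hypothesis 4 could be examined one variable at a time. This limits the over-adjustment problem to models that contain both technique and the symptom measures, which is what adjustment for the list implies. It does not touch reverse causation, which arises even with one variable at a time. Nor is this a matter of missing detail: the protocol fixes the list and the label, and its own schedule contradicts the label.

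Three stronger conclusions are tempting but not supported.

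- A reader might infer that the nine-variable model is too large for the number of events. The protocol gives no event risk and does not say that all nine variables enter one model.
- A reader might infer that patients recruited by letter have all their first measures at week 6. The Method section gives neither discharge dates nor letter dates, and invitation before discharge is the primary route, so neither the timing nor the share of such patients can be derived.
- A reader might infer that the reported associations will be badly biased. The schedule shows that the bias can arise, not how large it will be.

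**Conclusion.** The point holds as a contradiction between label and schedule. Of the nine variables called baseline in paper 4, one is known by surgery for every patient. The other eight are first scheduled on day 21 or day 42, against an adverse-event item taken at day 30. Carried out as written, the analysis could present consequences of complications as their predictors, and could adjust technique for its own effects.

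The conclusion rests on two readings, both stated above: that Table 1's weeks run from surgery, and that paper 4's adverse events are the 30-day item. The count of eight does not depend on how physical functioning is measured. The size of the bias cannot be calculated from the document. The correction should be made before paper 4 is analysed, but it concerns one planned paper and part of hypothesis 4, not the primary or secondary outcome.

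**What to change.** - In paper 4, do not adjust 30-day adverse events for any week-3 or week-6 measure.
- Adjust the technique comparison only for variables known by surgery and already collected: age, gender, tumour height, tumour stage, therapy given before surgery, and ASA grade if wanted. Name them in advance, keep them few because events may be few, and show the unadjusted comparison beside the adjusted one.
- When adverse events are the outcome, drop surgical complications and time with stoma from the adjusters in the Statistical analysis section. The first is part of the outcome, and the second accrues after surgery.
- For associations of week-3 or week-6 measures with mortality, start follow-up at the measurement and count only later deaths.
- Call these measures early post-operative, not baseline, throughout: in the Purpose, in hypothesis 4, and in papers 1, 3 and 4. State the origin of the weeks in Table 1.
- Restrict the adverse-event part of hypothesis 4 to variables known by surgery. Report differences in mortality and adverse events with 95% confidence intervals, and do not take non-significance as evidence of no difference.

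No new data are needed. The cost is that paper 4 loses eight of its nine listed predictors for adverse events, hypothesis 4 has to be reworded, and a short adjustment list may leave some confounding.
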